4.2.2 Study Day

Study days will be numbered relative to the first day of study drug administration.

- If the date of event is before the study drug administration, then:

Study day = (Date of measurement – Date of study drug administration in each group)

- If the date of event is on or after the study drug administration, then:

Study day = (Date of measurement – Date of study drug administration in each group) + 1

4.2.3 End of Study

The end of the study is defined as the date of the last visit of the last subject under the auspices of the current study.

4.2.4 Baseline

Baseline is defined as the last non-missing measurement recorded before first dose of the study drug administration for res.

Time-matched Measurements:

For Continuous 12-lead ECG using Holter's readings for Cardiac endpoints, baseline is defined as the time-matched measurements on Day -1.

No imputation will be done for missing baseline value for derivation of change from baseline or summary tables and shift tables.

4.2.5 Summary and Representation of Data

Continuous data will be summarized in terms of mean, standard deviation (SD), median, minimum, maximum and number of observations, unless otherwise stated.

Categorical data will be summarized in terms of the number of participants providing data at the relevant time point (n), frequency counts, and percentages.

The minimum and maximum will be reported to the same number of decimal places as the raw data recorded in the database. The mean and median will be reported to one more decimal place than the raw data recorded in the database. The SD will be reported to two more decimal places than the raw data recorded in the database. In general, the maximum number of decimal places reported shall be four for any summary statistics.

Percentages will be presented to one decimal place. Percentages will not be presented for zero counts. Percentages will be calculated using N as the denominator. If sample sizes are small, the data displays will show the percentages, but any textual report will describe frequencies only. Percentage will be presented as whole number if percentage is 100.

If for any summary table, n is less than three then only n, minimum, and maximum should be presented, and other summary statistics will be left blank.

All ECG data recorded during the course of the study or derived during the programming phase will be presented in the individual data listings. All listings will be presented sorted by treatment group, subject number, visit number, date and time point.

Abnormality on ECG parameters will be flagged using the flag system defined in [Table 4-2](#).

Unless specified otherwise, quantitative ECG parameters will be described per treatment group, day and time point using the following statistics: N (number of observations), mean, median, standard deviation (SD), minimum (Min), and maximum (Max) for raw and change from baseline values. 95% confidence interval (CI) of the mean will be added on changes from baseline.

4.3 Software

All report outputs will be produced using SAS® version 9.4 or later in a secure and validated environment.

The PK analyses will be conducted using Phoenix® WinNonlin (WNL) version 8.2 or later in a secure and validated environment.

All report outputs will be provided to the Sponsor in Microsoft RTF format.

4.4 Study Participants

4.4.1 Disposition of Participants

A clear accounting of the disposition of all subjects who enter the study will be provided, from randomization to study completion.

Subject disposition will be summarized by treatment group for the randomized analysis population. This display will show the number and percentage of subjects who have completed the study or have discontinued study treatment and a summary of the primary reasons for discontinuation of study treatment.

Primary reason for discontinuation of subjects are:

- Adverse event

- Withdrew consent
- Protocol deviation
- Loss to follow up
- Death
- Pregnancy
- Study terminated by sponsor
- Investigator decision
- Other

Disposition data will be presented for the Randomized Analysis Population.

Subject discontinuations will be listed including the date of study exit, details of IMP and reason for discontinuation in the randomized analysis population.

Listing of screening failure data will be provided including reason for screen failure in screened subjects. A disposition table during screening phase will also be provided in all screened subjects.

4.4.2 Protocol Deviations

All protocol deviations are predefined in the separate document, Protocol Deviation Specification.

4.4.2.1 Protocol Deviations with Non-PK Implications

The defined protocol deviations will be collected during the study period by site monitor/clinical team and programming team. All deviations related to study inclusion or exclusion criteria, conduct of the study, participant management or participant assessment, and handling of the participant's rights will be described.

4.4.2.2 Protocol Deviations with PK Implications

Protocol deviations that may potentially impact PK parameter derivations include, but are not limited to:

- Emetic episode in case of orally administered study drug
- IV administration deviations – interruption of administration, etc.
- Missed PK samples that impact estimation of PK parameter(s)
- Concomitant medications not authorized by protocol
- PK samples obtained out of allowance window that may impact the estimation of PK parameter(s)

Protocol deviations (mentioned in Sections 4.4.2.1 and 4.4.2.2) and analysis population will be reviewed in the data review meeting to decide inclusion or exclusion of participant(s) from analyses Population. Decisions regarding the exclusion of participants and/or participant data from analyses will be made after database lock and receipt of PK data, and will be documented and approved.

A by-participant listing of major and minor protocol deviations will be provided including participant identifier; exclusion from specific analysis population; and protocol deviation classification, and protocol deviation description and exclusion from specific analysis Population.

4.5 Analysis Populations

The following populations are defined for this study:

- **Randomized Population:** All participants who signed Informed Consent Form (ICF) and are assigned a randomization number are included in the randomized population.
- **Safety Population:** all subjects who received at least one dose of study drug (SC setmelanotide, SC placebo, oral moxifloxacin, or oral placebo).
- **Pharmacokinetic Population:** all subjects who received at least 1 dose of setmelanotide or moxifloxacin and have at least one quantifiable concentration of setmelanotide or moxifloxacin. A subject may be excluded from the PK summary statistics and statistical analysis if the subject has an AE of vomiting that occurs at or before 2 times the median T_{max} during moxifloxacin dosing.
- **ECG Population:** all subjects in the Safety Population with measurements at baseline as well as on-treatment with at least one post-dose timepoint with a valid value. The ECG population will be used for the by-timepoint and categorical analyses of the cardiodynamic ECG parameters.
- **PK/QTc Population:** all subjects who are in both the ECG and PK populations with at least 1 pair of post-dose PK and QTcF data from the same timepoint as well as subjects in the ECG population who received placebo. The PK/QTc population will be used for the C-QTc analysis. The PK/QTc population will be defined for setmelanotide and for moxifloxacin. Placebo subjects will be included in the C-QTc analysis set by setting their concentrations to 0.

A summary table with the number of participants in each of the analysis population will be provided and this table will be displayed by treatment group and overall, for randomized population. A listing of subjects excluded from analysis population will also be provided including reason of exclusion for randomized analysis population.

4.6 Demographics and Baseline Characteristics

The demographic characteristics (age, race, ethnicity, sex, height, body weight, body mass index [BMI]) will be summarized by treatment group and listed by participant for the Safety Population.

Age, height, BMI and weight will be summarized using the mean, SD, minimum, median, and maximum. The count and percentage will be computed for sex, race, and ethnicity. The summary table will be displayed by treatment group and overall, for the Safety Population.

4.7 Medical History

Based on the Safety Population, all subjects who had prior medical history will be presented in a by-subject listing including but not limited to subject ID, group, description of disease/procedure, MedDRA System Organ Class (SOC), MedDRA Preferred Term (PT), start date and stop date (or ongoing if applicable) of disease/procedure. All medical history will be coded using the Medical Dictionary for Regulatory Activities (MedDRA). The version used for coding will be identified in the Data Management Plan.

4.8 Concomitant Medications

Medications will be considered as concomitant if they are taken at least once in the treatment period

starting with the first study administration and ending after the last study drug administration during the study.

Medications will be coded using the latest version of World Health Organization-Drug Dictionary (WHO-DD) and will be classified by Anatomical Therapeutic Chemical (ATC) categories.

By-participant listings of prior and concomitant medications will be provided for the Safety Population .

4.9 Treatment Exposure and Compliance

4.9.1 Treatment Exposure

A by-participant listing of participant exposure to study drug will be generated. The listing will include dose, date and time, unit, formulation, route, and frequency.

4.9.2 Compliance

Not applicable.

4.10 Efficacy Evaluation

Not Applicable.

4.10.1 Analysis and Data Conventions

Not Applicable.

4.10.2 Primary Cardiac Variable

4.10.2.1 Cardiodynamic ECG Assessment (Concentration-QTc analysis)

Primary concentration-response relationship will be investigated between $\Delta QTcF$ measurements and setmelanotide concentration. The same methodology can be used to analyze other ECG parameters (HR, PR, QRS) if an effect was evidenced from the central tendency analysis.

The C-QTc analysis will be performed according to the methodology detailed in Garnett et al.() white paper.

4.10.2.1.1 Graphical exploratory analysis

As a preliminary step, graphical exploration supporting model assumptions will be performed as detailed in [Table 4-1](#).

Table 4-1 Graphical exploration analysis

Model assumption tested	Plot	Investigation	Model Impact
No drug effect on HR	Time course of mean HR/ΔHR stratified by dose (Day 10 vs. 16) Time course of estimated ΔΔHR stratified by dose (Day 10 vs. 16)	Homogeneous pattern between doses. No dose-related trend	Relationship between QT and RR may differ between on- and off treatment. The QTc correction could be inadequate on-treatment
QTc is independent of HR: Adequacy of the QTc correction in the population	Drug-free and/or placebo data: Scatter plot of QTc (y-axis) versus HR (x-axis) for baseline and placebo data with a regression line	The regression line should tend toward a horizontal line and show the lack of relationship between QTc and HR	Correction factor is potentially poorly estimated due to narrow range of HR intervals within each subject which could bias the C-QTc model. An alternative correction obtained on wider range of HR should be investigated (see section 4.10.2.1.2)
No Impact of a treatment effect on HR on the correction method	Change in QTc is independent of change in HR on-treatment: Scatter plot of on-treatment ΔQTc (y-axis) versus ΔHR (x-axis) with a regression line	The regression line should tend toward a horizontal line and show the lack of relationship between ΔQTc and ΔHR	The QTc correction could be inadequate on-treatment and could bias the C-QTc model. An alternative correction taking better into account HR variations should be investigated (see section 4.10.2.1.2)
Direct effect assumption. Impact of metabolite PK/PD hysteresis	Time course of GM concentrations and ΔΔQTc intervals	Shape of time course of effect, matched time of peaks, return to baseline Magnitude of variability in PK and QTc	Direct concentration-response model is inadequate. Alternative model (inclusion of metabolite, effect compartment, turn-over models) should be considered.
Drug effect on QTc	Time course of mean QTc/ΔQTc stratified by dose (Day 10 vs. 16)	Heterogeneity pattern between doses. Dose-related trend	A priori none since high inter-subject variability in ΔQTc can mask signal in mean curves.

Model assumption tested	Plot	Investigation	Model Impact
	Time course of estimated $\Delta\Delta QTc$ stratified by dose (Day 10 vs. 16)		However, largest $\Delta\Delta QTc$ should be consistent with $\Delta\Delta QTc$ predicted from the C-QTc model if the model is correct
Evaluate linearity and heterogeneity assumptions between exposure and QTc across doses and studies	C- ΔQTc : Scatterplot of individual ΔQTc (y-axis) vs. time-matched concentrations (x-axis) including a nonparametric trend curve	Shape of C-QTc relationship. Magnitude of ΔQTc over observed concentration range. Concentration range versus known clinical exposure scenario (therapeutic dose, worst case exposure, etc.)	A non-linear pattern could bias the C-QTc model and predictions. An alternative model should be envisaged Heterogeneity between doses/trials that should be taken into account in the C-QTc model

4.10.2.1.2 Study specific QT correction

For all analyses performed on healthy volunteers, the preferred, *a priori*, heart-rate correction method is the Fridericia -corrected QT interval (QTcF).

In the case that the individual correction factor is poorly estimated (due to narrow range of RR/HR intervals within each subject) or that setmelanotide has a chronotropic effect (resulting in change of HR after drug administration and a relationship between QT and RR that may differ between on- and off-treatment) it might be necessary to determine an alternative correction method for the QT interval in order to limit the bias in the assessment of QT/QTc prolongation.

In such case, an individual QT correction, QTcI, will be obtained from data recorded at baseline (Day -1) and from placebo subjects by modelling the QT/RR relationship (general power model) using a mixed model. The formula obtained for the QT/RR relation will then be converted to individual heart rate correction formulae.

The individual prediction of model parameters will be then applied to the QT and RR parameters at each time point to form the QTcI intervals.

The general power model relating QT and RR intervals can be written as follows:

$$QT = \alpha(RR/1000)^\beta, \alpha \text{ and } \beta \text{ being the model parameters to be estimated.}$$

After log transformation the model can be expressed as:

$$\text{Log}(QT) = \alpha' + \beta \text{log}(RR/1000), \text{ where } \alpha' = \log(\alpha).$$

In order to estimate the parameters, log(QT) and log(RR/1000) obtained at baseline and in placebo subjects will be submitted to a mixed regression model where the slope and the intercept will be considered as random terms.

The statistical expression of the mixed model is:

$$\text{Log}(QT_{ij}) = a_i + b_i \text{log}(RR_{ij}/1000) + e_{ij}$$

Where:

$\text{log}(QT_{ij})$ and $\text{log}(RR_{ij})$ are respectively, the j^{th} log QT/RR measurements performed on subject i

a_i and b_i are the random intercept and slope, respectively

4.10.2.1.3 Model development

The model development will start with the pre-specified mixed linear model as detailed in Garnett *et al* considering $\Delta QTcF$ as dependent variable. In case of the graphical exploration suggests that Fridericia correction does not account properly for HR/RR variations, alternative corrections should be investigated if possible (refer to previous Section 4.10.2.1.2).

The fixed effect parameters of the pre-specified model will be intercept, slope for linear effect of setmelanotide concentrations, influence of baseline (centered on mean) covariate, treatment specific intercept (0=placebo, 1=setmelanotide) and time (as factor).

Subject-specific random effects (between subject variability) will be added on intercept and slope parameters with an unstructured covariance matrix. In case of the unstructured covariance matrix is not supported by the data, other simplified or reduced structures will be investigated (ex. variance components).

$$\Delta QTcF_{ijk} = (\theta_0 + \eta_{0,i}) + (\theta_1 + \eta_{1,i})C_{ijk} + \theta_2 TRT_j + \theta_3(QTcF_{ijk=0} - \overline{QTcF_0}) + \theta_{4,k} Time_k + \varepsilon_{ijk} \quad (\text{Eq.1})$$

Where

- i is the subject, j the treatment and k the time;
- $\Delta QTcF_{ijk}$ is the change from baseline in QTcF for subject i in treatment j at time k ;
- θ_0 is the population mean intercept in the absence of a treatment effect;
- $\eta_{0,i}$ is the subject-specific random effect associated with the intercept term θ_0 ;
- θ_1 is the population mean slope of the assumed linear association between concentration and $\Delta QTcF_{ijk}$;
- $\eta_{1,i}$ is the subject-specific random effect associated with the slope θ_1 ;
- C_{ijk} is the concentration for subject i in treatment j and time k ;
- TRT_j is variable associated with treatment ($j=0$ for placebo subjects, $j=1$ for setmelanotide subjects);
- θ_2 is the fixed effect parameter associated with the treatment specific intercept TRT_j ;
- θ_3 is the fixed effect parameter associated with baseline and $\overline{QTcF_0}$ is the mean of all baseline;
- $\theta_{4,k}$ is a vector of $k-1$ parameters associated to the time factor, $Time_k$, having K levels. Time is defined as the scheduled time after dose;
- The influence of Day and the interaction between time and Day will be investigated within the model.
- $QTcF_{ijk=0}$ is the baseline QTcF

It is assumed the random effects are normally distributed with mean [0,0] and an unstructured covariance matrix G , whereas the residuals are normally distributed with mean 0 and variance R .

No additional covariate investigation will be performed and in order to avoid unnecessary model-building steps, non-significant fixed parameters will not be removed from the model. Random effects not supported by the model or resulting in null estimates will be removed as they may result in non-convergence problems.

The selection of best model will be based on AIC criteria.

The estimated mean, $\Delta\Delta QTcF$ and their 2-sided 90% confidence intervals will be calculated at each setmelanotide dose C_{\max} geometric means (C_d) as follows (Est refers to an estimate from the model):

- $\Delta\Delta QTcF(C_d)_{\text{Est}} = \theta_{2,Est} + \theta_{1,Est} C_d$
- 90% CI = $\Delta\Delta QTcF(C_d)_{\text{Est}} \pm t(0.95, DF) \times SE_{\text{Est}}$
- With $SE_{\text{Est}} = \sqrt{var(\theta_{2,Est}) + C_d^2 var(\theta_{1,Est}) + 2C_d cov(\theta_{2,Est}, \theta_{1,Est})}$

4.10.2.1.4 Model evaluation

Goodness of fit plots will be provided, consisting on:

- Quantile-Quantile plots of residuals;
- Concentrations versus residuals;
- Time, baseline and treatment versus residuals;
- Model predicted ΔQTc versus observed ΔQTc plotted versus with a regression line.

Any marked bias in residual plots may suggest model misspecification. Moreover, a large and significant treatment specific intercept (TRT term in the model) may also indicate model misspecification (i.e. lack of linearity or hysteresis).

Evaluation of the final model will be performed using:

- Visual predictive checks (VPC) obtained by simulating ΔQTc according to the final model selected and generated by binning the concentrations into deciles. VPC will be performed to assess the adequacy of the structural model.
- Mean observed and predicted ΔQTc by deciles of concentrations (quantile plot) with model slope and 90% CI.

4.10.2.1.5 Alternative to direct linear model

➤ Nonlinear model

In case of the linear relationship between ΔQTc and setmelanotide concentrations cannot be accepted, an alternative model such as saturable model will be considered:

$$\Delta QTc F_{ijk} = (\theta_0 + \eta_{0,i}) + \frac{(\theta_1 + \eta_{1,i})C_{ijk}^{\gamma}}{(\theta_2 + \eta_{2,i})^{\gamma} + C_{ijk}^{\gamma}} + \theta_3 TRT_j + \theta_4 (QTc F_{ijk=0} - \overline{QTc F_0}) + \theta_{5,k} Time_k + \varepsilon_{ijk}$$

(Eq.2)

In Eq.2, the parameter θ_1 is the maximum asymptotic effect due to treatment, and the parameter θ_2 is the concentration at which the effect is half θ_1 .

In that case, the mean and 90% CI for $\Delta\Delta QTc$ can be computed by non-parametric bootstrap methods with subject identifier used as the unit for resampling. Resampling should be stratified by dose level within the treatment group and the placebo subjects. Model parameters and $\Delta\Delta QTc$ are determined from each of the replicate bootstrapped datasets. Two-sided 90% CIs are computed from the 5th and 95th percentile of the rank-ordered $\Delta\Delta QTc$ values from all replicates.

➤ Indirect relationship

If the effect cannot be directly related (time-matched) to exposure to setmelanotide, it will be investigated whether any metabolite can explain the delayed effect.

In that case, a multivariate model combining parent and metabolite, as a linear or non-linear contribution, will be investigated using the same methodology as described above.

With such model, predictions of $\Delta\Delta QTc$ (and 90% CI) will be performed independently at C_{max} GM of each compound, setting the components for the other compounds at the mean value obtained at time of occurrence of C_{max} (t_{max}) of the compound of interest.

If the inclusion of the metabolite is not sufficient to explain the indirect/delayed effect and a hysteresis phenomenon cannot be ruled out, alternative models such as effect compartment or turn over models combining population PK and PKPD models should be envisaged. Such kind of modelling is out of the scope of this analysis plan and if it must be implemented will be detailed in a specific modelling plan.

4.10.2.1.6 Display of results

Parameters estimated from the selected model will be tabulated with their standard errors and 95% CIs. $\Delta\Delta QTc F$ predicted for each dose level will be presented with their 2-sided 90% CIs and a

graphical display of predicted $\Delta\Delta QTcF$ over the concentration range observed during the study will be provided.

4.10.2.1.7 Decision rule

The impact of setmelanotide on QT/QTc prolongation will be considered as below the threshold of regulatory concern if the upper bound of the 90% confidence interval of $\Delta\Delta QTcF$ predicted at highest dose C_{max} is below 10 ms.

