1. SYNOPSIS

Name of Sponsor/Company: Rhythm Pharmaceuticals, Inc.		
Name of Investigational Product: IMCIVREE™ (setmelanotide) injection		
Name of Active Ingredient: Setmelanotide (RM-493; Melanocortin-4 Receptor Agonist)		
Protocol Number: RM-493-032	Phase: 4	Country: USA
Title of Study: A Randomized, Double-Blind, 3-arm, Parallel Group, Placebo- and Positive -controlled Study to Investigate the Effects of Setmelanotide on QTc Interval in Healthy Subjects		
Study center(s): [REDACTED]		
Principal Investigator: [REDACTED]		
Studied period (years): Estimated date first subject enrolled: September, 2021 Estimated date last subject completed: March, 2022		
Objectives: Primary: 
To evaluate the effects of therapeutic and supratherapeutic setmelanotide concentrations on QTc corrected by the Fridericia method (QTcF) interval in healthy subjects. Secondary: 
To assess the effects of therapeutic and supratherapeutic setmelanotide concentrations on heart rate (HR), PR interval, QRS interval, T-wave morphology, and cardiac safety in healthy subjects.To evaluate assay sensitivity and the effect of a positive control, a single 400 mg oral dose of moxifloxacin, on the QT/QTcF interval in healthy subjects.To assess the pharmacokinetics (PK) of setmelanotide following administration of therapeutic and supratherapeutic doses of subcutaneous (SC) setmelanotide in healthy subjects.		

- To evaluate the safety and tolerability of therapeutic and supratherapeutic doses of SC setmelanotide in healthy subjects.

Methodology:

[figure not shown]
This is a double-blind, randomized, placebo- and positive-controlled, parallel group, 3-arm study to assess the potential for therapeutic and supratherapeutic concentrations of setmelanotide to affect the QTcF interval compared with placebo. SC setmelanotide doses will be titrated throughout the study (2 mg \times 7 days, 3 mg \times 3 days, 5 mg \times 3 days, and 7 mg \times 3 days) to reduce the potential of experiencing gastrointestinal effects previously observed at initiation of treatment and to titrate to higher doses. Oral moxifloxacin will be used as a positive control to establish the assay sensitivity of this study.

Approximately 72 healthy adult male and female subjects will be enrolled and randomized 1:1:1 to 1 of 3 groups:

- **Group 1:** SC setmelanotide; oral placebo on Days 10 and 16

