11. STATISTICS

11.1. Sample Size Determination

11.1.1. Sample Size for Setmelanotide C-QTc Analysis

A sample size of 60 evaluable subjects who complete the study (20 subjects in Group 1 receiving SC setmelanotide and 20 subjects each in Groups 2 and 3 receiving SC placebo) will provide at least 85% power to exclude that setmelanotide causes more than 10 msec QTc effect at clinically relevant plasma levels, as shown by the upper bound of the 2-sided 90% confidence interval (CI) of the model-predicted QTc effect ($\Delta\Delta\text{QTcF}$) at the observed geometric mean Cmax of setmelanotide on Day 10 and Day 16 in the study individually. This power is estimated approximately using a 2-sample t-test using nQuery 8 (www.statsols.com). The calculation assumes a 1-sided 0.05 significance level, a small underlying effect of setmelanotide of 3 msec and a standard deviation (SD) of the ΔQTcF of 8 msec for both SC setmelanotide and SC placebo. Note that this calculation is conservative, since it does not take into account any gain in precision due to the use of all data from each subject with the help of a linear mixed effects model. The concentration-QTc analysis method is supported by [Darpo \(2015\)](#) and [Ferber \(2015\)](#).

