11.3.1. Cardiodynamic ECG Assessment

The primary analysis will be based on C-QTc modeling of the relationship between plasma concentrations of setmelanotide (or placebo) and $\Delta QTcF$ (using Day -1 time-matched Holter ECGs as baseline) with the intent to exclude an effect of $\Delta\Delta QTcF > 10$ msec at clinically relevant plasma levels, using the concepts presented in the “Scientific White Paper on C-QTc modeling” (Garnett 2018b, Garnett 2018a). After development of the C-QTc model and assessment of model performance through nonparametric bootstrapping, the $\Delta\Delta QTcF$ associated with the Cmax of therapeutic and supratherapeutic doses will be computed using bias-corrected 90% CI. An increase in QTc of ≥ 10 msec can be ruled out if the upper 90% CI is < 10 msec.

The change from baseline (Δ) and placebo-corrected change from baseline ($\Delta\Delta$) QTcF, HR, PR, and QRS will be summarized by nominal time and treatment using descriptive statistics. An analysis of categorical outliers will be performed for changes in QTcF, HR, PR, and QRS, and T-wave morphology, and U-wave presence and results will be summarized.

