11.3.2. Assay Sensitivity

Assay sensitivity will be evaluated by C-QTc analysis of the effect on $\Delta\Delta QTcF$ of moxifloxacin using a similar model as for the primary analysis. Assay sensitivity will be deemed as met if the predicted QT effect (i.e., the lower bound of the 2-sided 90% CI of $\Delta\Delta QTcF$) is above 5 msec at the observed geometric mean Cmax of 400 mg oral moxifloxacin.

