4.10.3.3 Assay sensitivity

The moxifloxacin C-QTc model will follow the same methods as described for setmelanotide model from Section 4.10.2.1.1 to 4.10.2.1.4. The sensitivity analysis will be performed separately for day 10 and day 16, due to the different baseline for moxifloxacin in group 2 and 3.

The assay sensitivity will be accepted if the slope for the relationship is significant at the 5% level and if the lower bound of the 90% CI of $\Delta\Delta\text{QTc}$ predicted at moxifloxacin C_{max} is above 5 ms.

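### The rule that clears setmelanotide rests on its own 10 ms bound alone, so the study can reach that conclusion without having shown assay sensitivity

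*SAP*

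**What the plan says.** SAP 4.10.2.1.7 is a single sentence with a single condition. It starts "The impact of setmelanotide on QT/QTc prolongation will be considered as below the threshold of regulatory concern if the upper bound of the 90" and completes the condition as the 90% interval for ΔΔQTcF, predicted at the Cmax of the highest dose, lying below 10 ms. Protocol 11.3.1, repeated in the synopsis, says that an increase of 10 msec or more "can be ruled out if the upper 90% CI is" under 10 msec. Neither adds a further requirement.

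The synopsis gives the purpose of the control: "Oral moxifloxacin will be used as a positive control to establish the assay sensitivity of this study". The pass criterion is set elsewhere. Protocol 11.3.2 says "Assay sensitivity will be deemed as met if the predicted QT effect", taken as the lower bound of the two-sided 90% interval at the geometric mean moxifloxacin Cmax, exceeds 5 msec. SAP 4.10.3.3, placed under the secondary cardiac variables, keeps the 5 ms bound and adds a slope condition: "The assay sensitivity will be accepted if the slope for the relationship is significant at the 5% level". It also says "The sensitivity analysis will be performed separately for day 10 and day 16", without saying whether one day or both must pass.

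Neither document connects the assay-sensitivity result to the setmelanotide conclusion, and SAP 4.14 records no change to the planned analysis.

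**The concern.** A conclusion that an effect is smaller than 10 msec is a claim of absence. Anything in ECG acquisition or reading that blunts QT differences pushes the estimate towards that claim. The positive control is the design's safeguard against this, and two of the three groups take moxifloxacin to provide it. Under the rule as written the safeguard has no force: if assay sensitivity is not shown, the rule still returns the favourable conclusion. The weight given to the failure would then be settled after the results are known, in a study run to meet a postmarketing requirement (Protocol 3.2).

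**Working it through.** **Inputs.** Protocol 11.1.1 gives the setmelanotide assumptions: "The calculation assumes a 1-sided 0.05 significance level, a small underlying effect of setmelanotide of 3 msec and a standard deviation (SD) of the" change from baseline of 8 msec, with a 10 msec margin and 20 evaluable subjects per group. Protocol 11.1.2 gives a moxifloxacin effect of 10 msec, SD 8 msec and a threshold of 5 msec. The correlation between a subject's Day 10 and Day 16 values (ρ) is not given, so 0 and 0.5 are assumed.

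**1. Setmelanotide power.** SE = 8 × √(1/20 + 1/20) = 2.530. Noncentrality = (10 − 3)/2.530 = 2.767. With 38 df and one-sided 0.05, power is 85.8%, against a stated figure of at least 85%. It reproduces.

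**2. Assay-sensitivity power.**
- One day, 20 versus 20: noncentrality = (10 − 5)/2.530 = 1.976, power 61.6%. SAP 4.13 and the synopsis attach at least 81% to this comparison. It does not reproduce; 81% would need about 34 per arm. Protocol 11.1.2 attaches the 81% to the 40-subject crossover instead, where it is met.
- Pooled crossover, 40 subjects: SD of the within-subject difference = 8 × √(2(1 − ρ)).
  - At ρ = 0: 11.31, SE = 11.31/√40 = 1.789, noncentrality = 5/1.789 = 2.795, power 86.5%. This matches the stated 86%.
  - At ρ = 0.5: SD 8, SE = 8/√40 = 1.265, noncentrality = 5/1.265 = 3.953, power 98.7%.

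**3. The two results together.** Trials were simulated (40,000 per scenario) with t-based 90% intervals: setmelanotide 3 msec, moxifloxacin 10 msec, clearance judged on Day 16. Assay sensitivity was judged on the 5 ms lower bound only, without the SAP's slope condition. The rule as written clears setmelanotide in 85.7% (ρ = 0) and 86.0% (ρ = 0.5) of trials.

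| Assay-sensitivity analysis | Cleared and assay sensitivity shown (ρ = 0 / 0.5) | Cleared without it (ρ = 0 / 0.5) |
|---|---|---|
| Pooled crossover | 72.8% / 84.8% | 12.9% / 1.2% |
| Day 16 alone | 49.3% / 49.4% | 36.4% / 36.5% |
| Both days must pass | 30.4% / 25.9% | 55.3% / 60.0% |

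The two results are not independent, because both comparisons use the same placebo subjects. For Day 16 at ρ = 0, independence would give 0.857 × 0.618 = 53.0% cleared with assay sensitivity, against 49.3% simulated.

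**4. An assay that shows nothing.** With the true moxifloxacin effect set to 0, the rule as written still clears setmelanotide in 85.5–85.9% of trials. This follows directly from the rule, which never looks at moxifloxacin. A rule requiring assay sensitivity clears it in about 0%, whichever analysis is used.

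**The case against.** Assay sensitivity is not neglected. It is a secondary objective with its own sample-size statement and a fixed pass criterion, so a failure would be visible in the report. Protocol 11.3.1 can also be read as a statement about an interval, followed directly by the assay-sensitivity section, rather than as a verdict on the study. Changing the rule alters no data, model, estimate or interval. All of that stands. It does not answer the point, because SAP 4.10.2.1.7 is headed as the decision rule and leaves out the condition that the control was included to supply.

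Three stronger readings are tempting and should not be drawn.

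- **That the drug could be cleared in a study that did not detect moxifloxacin at all, with the failure rates above measuring how often.** The criterion is a lower bound above 5 ms, plus a slope condition in the SAP, which is stricter than detection. On the planning inputs, one day of 20 versus 20 has 98.7% power to put the lower bound above 0 (noncentrality 10/2.530 = 3.953). Non-detection is therefore about 1.3% per day, although missing the 5 ms bar is far more common.
- **That 12–16% of trials would give false reassurance.** A reader could reach this from the stated powers: 0.14 × 0.85 = 12% and 0.19 × 0.85 = 16%. But those powers are stated as minima, the product assumes independence, and the 81% does not reproduce for a single day. In that scenario the true setmelanotide effect is 3 msec, so clearing it is the right answer.
- **That the control guards against dosing errors with setmelanotide.** Moxifloxacin in Groups 2 and 3 cannot show how Group 1 was dosed. The measured setmelanotide concentrations do that, and they enter the primary model.

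**Conclusion.** The point holds. Both documents allow the setmelanotide conclusion on its upper 90% bound alone, so it can be returned when assay sensitivity has not been shown. If moxifloxacin truly has no effect, the rule clears setmelanotide in about 86% of trials, against about 0% for a rule with both conditions. At the planned 10 msec effect, clearance without assay sensitivity occurs in about 1–13% (pooled crossover, ρ from 0.5 to 0), about 36% (Day 16 alone) or about 55–60% (both days required). These are rates of a missed control beside a setmelanotide clearance, not rates of a wrong conclusion.

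The figures rest on the protocol's t-test approximation and planning values and on assumed correlations. The planned mixed model uses all time points and may be more precise. The SAP's added slope condition can only lower the chance of showing assay sensitivity. That the condition is missing from the rule depends on none of these assumptions.

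**What to change.** Reword SAP 4.10.2.1.7, Protocol 11.3.1 and the matching synopsis text along these lines: *the effect of setmelanotide is considered below 10 ms only if assay sensitivity has been shown and the upper 90% bound of ΔΔQTcF is below 10 ms; if assay sensitivity is not shown, the estimate and interval are reported and the result is called inconclusive.*

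The new condition cannot be applied until SAP 4.10.3.3 says which analysis decides it. The pooled Day 10/Day 16 crossover analysis is the natural choice. It is the one that supports the stated 86% power, and it fits Protocol 5.3, where subjects in Groups 2 and 3 act as their own controls. SAP 4.10.3.3 now separates the days because of differing baselines in those groups, so the pooled model must say how it handles that. The slope condition should also be made the same in both documents.

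The edit is a few sentences and needs no new data. The real cost is that the planned chance of a positive overall conclusion falls from about 86% to about 73–85% with the pooled analysis. It would be about 49% with Day 16 alone and 26–30% if both days must pass, so the choice should be fixed before unblinding and the sample-size text should quote the joint figure.
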